The R3 system offers four XLPE liner options – 0 degree, 20 degree, 0 degree +4 and 20 degree +4. Conventional polyethylene will not be offered. The Smith & Nephew 10 Mrad, fully annealed XLPE is the only cross-linked polyethylene proven to produce less volume of wear debris particles in all head size ranges. Less wear debris provides a chance for reduced osteolysis.

Metal-on-metal

Early experience with metal-on-metal (MoM) bearings validated the concept of this articulation surface for THA⁹. In particular, the wear properties of MoM bearings received greater attention as the limitations of MoP bearings became known. Although the long-term success of the McKee-Farrar and Ring THA systems is attributed in part to a high carbon cobalt chrome molybdenum (CoCrMo) alloy used to produce the devices in the 'as cast' metal, reasons for failures of these devices include the limitations of manufacturing methods at the time these devices were produced¹⁰. The newer MoM prostheses utilize improved bearing geometry and new surface finishings that promote lubrication. Mid-term follow-up on these prostheses demonstrates equivalent safety and effectiveness outcome compared to MoP prostheses¹¹. They offer the potential for greatly reduced wear. Metal bearings are available in several sizes. Large femoral heads can provide increased range of motion and greater stability, which can significantly reduce the risk of hip dislocation¹².

Superior metallurgy and optimal clearances, also used in the clinically proven, highly successful, world-leading BIRMINGHAM HIP Resurfacing System (BHR), provide the R3 Metal-on-Metal system superior performance. The R3 Metal-on-Metal and the

BHR system utilize high-carbide cobalt chrome in the as-cast micro-structural condition, providing superior wear resistance. The R3 provides specific metal inserts for large femoral head sizes (Ø38mm – 54mm heads in shell sizes 50mm – 68mm) which are either combined with the modular BHR heads or the BHR resurfacing.

3. Study Objective

The objective of this study is to determine the long-term safety and effectiveness of the R3 Acetabular System

Hypothesis: implant survivorship (Kaplan-Meier) (revision for any reason) of the R3 cup is at least 97% at 3 years, 95% at 5 years, 93% at 7 years, and 90% at 10 years follow-up.

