3.1. Study Design

This is a multicenter prospective observational post-market clinical follow-up study that will include 500 patients who will have total hip replacement with the R3 Acetabular System and either cemented or cementless hip stem.

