6.1. Device Components

The subject device hip system is consisting of R3 acetabular cups and three liners: metal, ceramic and XLPE. The modular femoral heads mate with existing, commercially-available Smith & Nephew Orthopaedics uncemented or cemented femoral stems.

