Smith and Nephew (S&N) is performing a multicenter prospective observational post-market clinical follow-up study that will include up to 500 patients who will have total hip replacement with the R3 Acetabular System and either cemented or cementless hip stem. The objective of this study is to determine the long-term safety and effectiveness of the R3 Acetabular System. The central hypothesis is that implant survivorship of the R3 cup is at least 97% at 3 years, 95% at 5 years, 93% at 7 years, and 90% at 10 years follow-up per Kaplan Meier analysis.

Device Components

The R3 system was designed to provide the ability to tailor the implant to the individual patient requirements. The R3 system is currently available with no-hole and three-hole shells with and without HA coating and its shells have a hemispherical design. For an improved primary and secondary stability, the R3 has a porous coating called Stiktite. This coating contains sintered asymmetric titanium grains, which allows for an enhanced scratch fit and stability.

The hip system used in this study consists of R3 acetabular cups and three liner options: metal (CoCr and Oxinium), ceramic (BIOLOXforte and BIOLOXdelta) and XLPE. The modular femoral heads mate with existing, commercially-available Smith & Nephew Orthopaedics uncemented or cemented femoral stems.

Goal of Radiographic Analysis

One of the safety measures in this study is the radiographic analysis of the operated hip over time. This includes surgery- and device-related events such as device revision, component failure, malfunction, migration or loosening that can be assessed by radiograph. Some events may not be evident until after a long-term follow-up such as evidence of severe osteolysis, excessive articular surface wear, or significant debris production.

Imaging Time Points

AP and lateral radiographs will be obtained before discharge in addition to at 1 year, 3 years, 5 years, 7 years and 10 years postoperatively. Additionally, the 1-year follow-up radiograph set includes a full pelvic overview (including at least 20 cm of the proximal femur).

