Although the AP pelvic image is preferred for determining migration, if the image is not available or is of poor quality, the AP hip view may be used to determine cup migration. In the AP hip image, a reference to the horizontal axis will be used to measure the horizontal distance between the midpoint of the lateral edge of the metal shell and a line drawn through the center of the teardrop. Movement along the vertical axis will be determined by measuring the distance from the midpoint of the edge of the metal outer shell to a line tangent to the inferior edges of both teardrops on the AP pelvic view.

Stem Fixation:

Stem fixation - uncemented stems (Engh et al)
not applicable
fixation by bone ingrowth
stable fibrous ingrowth
unstable implant

[figure not shown]
Only uncemented stems will be used in this study. There are three options for stem fixation assessment: fixation by bone ingrowth, stable by bone ingrowth, and unstable implant. Further definition of each of these terms follows:

- Fixation by bone ingrowth
 - Spot welding (new bone formation contacting the prosthesis) and absence of lucent lines next to porous coating
- Stable fibrous ingrowth:
 - Unchanged radiolucent lines at bone-metal interface measuring <2 mm in width, often associated with a sclerotic line
- Unstable implant
 - Progressive increase in radiolucent lines at the bone-metal interface, component migration, or pedestal formation (bony hypertrophy around tip due to stress loading)

Heterotopic Ossification:

Hete	erotopic ossification (Brooker Classification) (Tick one box only)
	Grade 0 none, no islands of bone
	Grade I islands of bone within the soft tissues about the hip
	Grade II bone spurs from the pelvis or proximal end of the femur leaving at least 1 cm between opposing bone surfaces
	Grade III bone spurs from the pelvis or proximal end of the femur, reducing the space between opposing bone surfaces to less than 1 cm
П	Grade IV apparent bone ankylosis of the hip

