 where Y is the exact (known) value

As a result of these discrepancies, any quantitative measurements performed on the radiographs using the existing CF, could produce a 15-54% error. For example, a measured radiolucent line of 2.2 mm on the lateral image is actually only 1.12 mm. Since the CRF bins radiolucent lines in buckets of "0 up to 1mm", "1 up to 2 mm", and "> 2 mm", data would have been entered incorrectly (a check in the "> 2 mm" box instead of the correct box of "1 up to 2 mm").

To ensure image headers contain an accurate CF, an additional evaluation step will be implemented for all images in this study followed by recalibration if necessary.

Procedure for the Evaluation Step:

Step 1: Each radiograph will be opened (Figure 2). The femoral head of the implant will be magnified (Figure 3) and a best-fit circle will be drawn around the femoral head to determine its diameter in pixels. Three points on the femoral head will be selected in order to create the circle (Figure 4, arrows highlight the 3 points selected).

Step 2: The diameter of the circle in pixels will be calculated and output to a spreadsheet for each image. The image name (containing the patient ID, time point, date of acquisition, and radiographic view) will also be exported with the diameter. In addition, the type of image (DICOM or TIFF) and original embedded scale factor (for DICOM only) will be copied from the headers into the spreadsheet.

Step 3: The actual diameter of the femoral head for each implant, as reported by S&N's product development team, will be reported in the same spreadsheet. The diameter is specific to the implant size and material (Table 1) and is specific to the individual patient.

Step 4: The CF will be calculated by dividing the actual femoral head diameter (in mm) by the diameter of the head (in pixels) measured in Step 1. The resulting number is the CF in units of mm/pixel. This number will allow conversion between pixels and mm for any measurement on a given image. Figure 5 is a snapshot of the spreadsheet layout.

[figure not shown]

Table 1: Femoral Head Diameters

Figure 5	Size	Outside Diameter (mm)
	28	27.9
	32	31.9
OXINIUM	36	35.9
	40	39.9
	44	43.9
	22	22.2
	26	25.9
	28	27.9
CoCr	32	31.9
	36	35.9
	40	39.9
	44	43.9
	28	28.0
Biolox Forte	32	32.0
	36	36.0
	28	28.0
Biolox delta	32	32.0
	36	36.0

Image Name	File Type	Reported Pixel Spacing (mm)	Known Length (mm)	Measured Length (pixels)	Actual Pixel Spacing (mm)

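### The image protocol tells the central reader that all stems are uncemented and omits the form's 'not applicable' box, although the study permits cemented stems, so a cemented stem could be graded on the ingrowth scale

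*Combined protocol and SAP*

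**What the plan says.** On stem type the documents give two answers.

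- Protocol Section 3.1 describes patients receiving "either cemented or cementless hip stem".
- Protocol Section 6.1 pairs the modular heads with "commercially-available Smith & Nephew Orthopaedics uncemented or cemented femoral stems".
- The Image Evaluation Protocol, Study Summary, describes "total hip replacement with the R3 Acetabular System and either cemented or cementless hip stem", and its Device Components paragraph repeats the point: "The modular femoral heads mate with existing, commercially-available Smith & Nephew Orthopaedics uncemented or cemented femoral stems".
- The same image protocol, under Stem Fixation, says "Only uncemented stems will be used in this study".

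The Stem Fixation text then says "There are three options for stem fixation assessment" and names bone ingrowth, a second grade labelled as stable by bone ingrowth, and unstable implant. The form field beside it is headed for uncemented stems and has four boxes: not applicable, fixation by bone ingrowth, stable fibrous ingrowth and unstable implant. The definitions under the instruction also use the fibrous label for the second grade.

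On calibration, Appendix B of the image protocol rescales each image from the known femoral head diameter. Step 3 says: "The diameter is specific to the implant size and material (Table 1) and is specific to the individual patient".

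**The concern.** The central reader works from the image protocol. Its Stem Fixation text asserts that no cemented stem exists and leaves out the one box that would suit a cemented stem. The reader is thus given no reason to tick that box. The grades rest on signs of bone growing onto a porous surface and on lucent lines at the bone-metal interface, which do not describe how a cemented stem is held. A cemented stem with no lucent lines would probably fall nearest to bone ingrowth, the most favourable grade.

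At stake is the fixation grade in the full R3 cohort. The image protocol counts radiographic analysis among the study's safety measures. If cemented stems are mixed into the ingrowth grades, the summary no longer describes uncemented fixation.

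**Working it through.** The plan gives no figure to reproduce, so the check is mainly a comparison of texts.

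**1. Is the contradiction real?** Four places permit cemented stems: protocol 3.1 and 6.1, and the image protocol's Study Summary and Device Components. One place, Stem Fixation, denies them. Two of the four are in the same document as the denial.

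**2. Does the denial reach the whole cohort?** Imaging Time Points says that, when the current statement of work ends, every patient in the R3 study will have been read at discharge and at years 1, 3 and 5. The instruction is therefore not confined to the ceramic-on-ceramic post-approval group.

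**3. Could the general form rules rescue the reader?** The Case Report Form Completion Instructions require every field to be filled before sign-off. The standard reasons for an unavailable field all concern the image: missing, badly exposed, outside the field of view, or wrongly positioned or projected. None concerns implant type. The remaining safeguard is the form itself. Its field is headed for uncemented stems, and the 5- and 7-year forms show the 'not applicable' box.

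**4. How large could the effect be?** Let N be the stems summarised, C the cemented stems among them, and r the true ingrowth proportion among the uncemented stems. At worst, every cemented stem is graded as bone ingrowth:

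- reported proportion = [r(N − C) + C] / N
- excess over r = (C/N)(1 − r)

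If every cemented stem is marked 'not applicable' and left out, the excess is 0. The documents give neither C nor r, so the effect lies between 0 and (C/N)(1 − r) and cannot be narrowed further.

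**5. Head-diameter table.** The protocol's Introduction describes metal inserts for 38–54 mm heads. Appendix B Table 1 lists CoCr heads of 22, 26, 28, 32, 36, 40 and 44 mm. From 38 to 54 mm there are 54 − 38 + 1 = 17 whole-millimetre sizes, of which 9 are even. Table 1 lists 2 of them, 40 and 44. Step 4 sets the conversion factor as

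- factor (mm/pixel) = actual head diameter / measured diameter in pixels.

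The relative scale error is (diameter entered / true diameter) − 1. Step 3 enters the actual diameter for each implant, as supplied by the sponsor's product development team, so the error is 1 − 1 = 0 for any head size. The formula has no upper limit, and Appendix B applies the step to all images.

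**The case against.** The strongest reply is that a correct answer is already on the form. The field heading restricts the scale to uncemented stems, and 'not applicable' is offered. Enrolment has closed and many images are retrospective, so the sentence may simply report that no cemented stem was implanted. Section 9 of the protocol plans no comparison between stem types, and fixation grade is not part of the post-approval study's radiographic success.

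Much of this stands. It rules out saying that patients received wrong grades. It does not remove the conflict: the instruction contradicts its own document, omits a box on its own form, and mislabels a grade. The documents do not settle whether cemented stems were used.

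A reader might also infer that patients with large metal heads have uncalibrated millimetre readings, because Table 1 stops at 44 mm. The documents do not support that. The image protocol says that the head diameter is known for each patient, and Steps 3 and 4 use that value. Appendix B's 15–54% error describes the embedded scale factor before correction, and no text sends unlisted heads back to it. Entering a 54 mm head as 43.9 mm would give 43.9/54 − 1 = −18.7%, so a true 5 mm would read 4.06 mm, but nothing directs anyone to do so. The 38–54 mm range is itself introductory product description, and it also covers heads used with a resurfacing device. It does not show which sizes were implanted.

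**Conclusion.** The Stem Fixation instruction is wrong as written, because it conflicts with protocol 3.1 and 6.1 and with the image protocol's own summary and device description. The supported consequence is a risk that cemented stems are graded on the uncemented scale, probably in the favourable direction. The size is unknown: zero if no cemented stem was implanted or the box was used correctly, and at most (C/N)(1 − r) on the reported ingrowth proportion under the worst case above.

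The stronger reading, that cemented stems have been misgraded, is not shown. Nor is any scale error from the gaps in Table 1, which are a matter of completeness only. Survivorship is not affected in either study. Angles do not depend on the scale factor. The post-approval definition of radiographic success uses lucency, subsidence and inclination and not the fixation grade. The ceramic-on-ceramic bearings (32 and 36 mm) are in Table 1.

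**What to change.** In the Image Evaluation Protocol, Stem Fixation:

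1. Reconcile the sentence on stem type with protocol 3.1 and 6.1 and with the Study Summary and Device Components, using the implant records to establish which stems were used.
2. List all four boxes, and tell the reader to tick 'not applicable' for any cemented stem.
3. Change the second grade's label in the instruction to stable fibrous ingrowth, as on the form and in the definitions.
4. State that cemented stems are left out of any ingrowth summary, with their number reported.
5. Check the fixation field for any cemented stem already read, and correct it if needed.

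As housekeeping, complete Table 1 for every head size actually implanted. Unlisted heads should not be marked 'Not Evaluable', since that would discard images that can be calibrated from the known diameter.

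The cost is a short revision of the image protocol, a look-up of stem type and head diameter in existing records, and re-entry for affected cases only. Imaging Time Points foresees a new statement of work for the 7- and 10-year reads, which is a natural moment for the change.

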Appendix A: Imaging Workflow

F465 R3 Acetabular System Study Established Workflow LEGEND

 where Y is the exact (known) value

As a result of these discrepancies, any quantitative measurements performed on the radiographs using the existing CF, could produce a 15-54% error. For example, a measured radiolucent line of 2.2 mm on the lateral image is actually only 1.12 mm. Since the CRF bins radiolucent lines in buckets of "0 up to 1mm", "1 up to 2 mm", and "> 2 mm", data would have been entered incorrectly (a check in the "> 2 mm" box instead of the correct box of "1 up to 2 mm").

To ensure image headers contain an accurate CF, an additional evaluation step will be implemented for all images in this study followed by recalibration if necessary.

Procedure for the Evaluation Step:

Step 1: Each radiograph will be opened (Figure 2). The femoral head of the implant will be magnified (Figure 3) and a best-fit circle will be drawn around the femoral head to determine its diameter in pixels. Three points on the femoral head will be selected in order to create the circle (Figure 4, arrows highlight the 3 points selected).

Step 2: The diameter of the circle in pixels will be calculated and output to a spreadsheet for each image. The image name (containing the patient ID, time point, date of acquisition, and radiographic view) will also be exported with the diameter. In addition, the type of image (DICOM or TIFF) and original embedded scale factor (for DICOM only) will be copied from the headers into the spreadsheet.

Step 3: The actual diameter of the femoral head for each implant, as reported by S&N's product development team, will be reported in the same spreadsheet. The diameter is specific to the implant size and material (Table 1) and is specific to the individual patient.

Step 4: The CF will be calculated by dividing the actual femoral head diameter (in mm) by the diameter of the head (in pixels) measured in Step 1. The resulting number is the CF in units of mm/pixel. This number will allow conversion between pixels and mm for any measurement on a given image. Figure 5 is a snapshot of the spreadsheet layout.

[figure not shown]

Table 1: Femoral Head Diameters

Figure 5	Size	Outside Diameter (mm)
	28	27.9
	32	31.9
OXINIUM	36	35.9
	40	39.9
	44	43.9
	22	22.2
	26	25.9
	28	27.9
CoCr	32	31.9
	36	35.9
	40	39.9
	44	43.9
	28	28.0
Biolox Forte	32	32.0
	36	36.0
	28	28.0
Biolox delta	32	32.0
	36	36.0

Image Name	File Type	Reported Pixel Spacing (mm)	Known Length (mm)	Measured Length (pixels)	Actual Pixel Spacing (mm)

Plate #060

> smith&nephew	Clinical Follow-up (page 1 of 2)	Project No: Study Patient No:	R3
5 Years	Date of Asses	ssment: Day	Month Year
Clinical follow-up done yes no			
General Findings			
Complications since last visit ☐ no ☐ yes Please complete adverse event form			
Charnley Classification (Tick one box only) A only ipsilateral hip involved			
☐ B both hips involved			
C other factors affecting locomotion			
Patients Opinion		(F)	
Satisfaction of patient (Tick one box only) □ very satisfied □ satisfied □ partly satisfied, partly dissatisfied □ dissatisfied □ very dissatisfied			
Radiographic Evaluation			
X-ray follow-up done			
yes no Reason:			
Notes:	this page as soon as complete	d	
PIRASE TAY	uus page as soon as complete	u	

Ī		I			I	I	I	ī	I		I		I			I	
																	- 1

DataFax #107

Plate #070

Visit #260

3:-	cmith&	nephew
-	Similia	CPITCH

Clinical Follow-up (page 2 of 2)

Project No:		R3
Study Patient No:		

	(page 2 of 2)						
5 Years Harris Hip Score							
Hip pain (Tick one box only) none or ignores it slight, minimal; no compromise in ac mild; following longer activities moderate; some limitations of activiti marked; serious limitations of activiti disabled; no activities possible, bedriven the public transportation (Tick one box yes, possible no, unable) Putting on shoes and socks (Tick one box with ease)	unable to sit comfortably Limp (Tick one box only) none dden slight only) moderate severe Leg length difference (Tick one box only)						
with ease with difficulty unable	ipsilateral shorter mm						
Distance walked (Tick one box only) ☐ unlimited, several hours ☐ six blocks, up to 2 km ☐ daily shopping, up to 500 m ☐ indoors only, up to 50 m ☐ bed / chair / not able to walk	Trendelenburg (Tick one box only) unable to test negative indifferent positive Range of motion (neutral-zero-method)						
Support (Tick one box only)	Flex / / / Ext						
 □ none □ single cane for long walks □ single cane most of the time □ one crutch □ two canes □ two crutches or not able to walk 	Abd / Add ER / IR						
Stairs (Tick one box only) ☐ foot over foot, without banister ☐ foot over foot, with banister ☐ in any manner ☐ unable							
Investigator's Signature: Date: Date:							
Places fav	this name as soon as completed						

DataFax # 107

Plate # 081

Visit # 260 5 Year

Independent Review X-ray Follow-up

(page 1 of 2)

Project No.: R3							
Study Patient No:							

	(, ,	
General Findings	Date of I	Radiograph: Day Month Year
migration medial	mm varus mm valgu o subsi	-
☐ not applicable☐ fixation by bone ingrowth☐ stable fibrous ingrowth☐ unstable implant		
**Compared to baseline post-o	perative	
☐ Grade 0 none, no islands of bo ☐ Grade I islands of bone within ☐ Grade II bone spurs from the p bone surfaces	the soft tissues about the hip belvis or proximal end of the femur leaving pelvis or proximal end of the femur, reduc m	
Investigator's Signature:		Date: Day Month Year
	Please fax this page as soon as complet	e

1		I	ľ		1	1					Ĩ		T	I			1	1	
		1	3			3	3	F 13	2			3	38.8		ž.	ž.			è

DataFax#107

Plate # 093

Visit#2605Year

smith&nephew	*	smith	&nep	hew
--------------	---	-------	------	-----

Independent Review X-ray Follow-up

Project No.: I	₹3		
Patient No:			

			(page 2	of 2)	rat	ient No.	
	Radiographic Evaluation						
Cnb	Radiolucent lines Negative	Osteolysis	Atrophy	oderate severe	Hypertroph minima	y Imoderate severe	
AP (0mm 1mm 2mm >2mm	no yes		2mm >2mm	none 1mm	2mm >2mm	1) 🗸 "
	Zone I						YAA.
	Zone II						1
İ							2 7
	Zone IV						6
LAT	Zone V						3 5
	Radiolucent lines	Osteolysis	Atrophy	,	Hypertroph	ıy	4
	Negative						
_	0mm 1mm 2mm>2mm	no yes	minimal mo none 1mm	oderate severe 2mm >2mm	minimal none 1mm	moderate severe 2mm >2mm	
ten	Zone 1						
AP Stem	Zone 2						7250
1	Zone 3						\
	Zone 4						IV VI
	Zone 5						W. VI
	Zone 6						8 14
İ	Zone 8						9 13
	Zone 9 🔲 🔲 🔲						10 12
	Zone 10						
	Zone 11						11
	Zone 12						
	Zone 13						
LAT	Notes:						
	Investigator's Signature:				С	Date: Day	Month Year
		Plea	se fax this page	as soon as co	mplete	,	

				I		The state of the s		I			1					ű.		
Da	taFax	#107	, -	_		Pla	ate #0	060	 			Visi	t #28	34				

> smith&nephew	Clinical Follow up	Project No:					
> smithanephew	Clinical Follow-up (page 1 of 2)	Study Patient No:					
7 Years	Date of Asses	ssment: Day Month Year					
Clinical follow-up done							
General Findings							
Complications since last visit no yes Please complete adverse event form							
Charnley Classification (Tick one box only) A only ipsilateral hip involved B both hips involved C other factors affecting locomotion							
Patients Opinion							
Satisfaction of patient (Tick one box only) very satisfied satisfied partly satisfied, partly dissatisfied dissatisfied very dissatisfied very dissatisfied							
Radiographic Evaluation							
X-ray follow-up done							
yes no							
Reason:							
Notes:							
Please fax	x this page as soon as complete	ea					

Ī																
Dat	aFax	#107			Pla	ate #0	070				Visi	t #28	34			

			2
-	smith	&nor	how
	21111111	KIIEL	VIICAA

Clinical Follow-up (page 2 of 2)

Project No:	R3
Study Patient No:	

7 Years	
Harris Hip Score	
Hip pain (Tick one box only)	Sitting (Tick one box only)
none or ignores it	comfortably in any chair 1 hour
slight, minimal; no compromise in activities	on a high chair for 1 1/2 hour
mild; following longer activities	unable to sit comfortably
moderate; some limitations of activities	Limon (Tide and bounds)
marked; serious limitations of activities	Limp (Tick one box only)
disabled; no activities possible, bedridden	none
_ , , , , , , , , , , , , , , , , , , ,	slight
Enter public transportation (Tick one box only)	moderate
yes, possible	☐ severe
no, unable	Leg length difference (Tick one box only)
Putting on shoes and socks (Tick one box only)	none
☐ with ease	ipsilateral longer mm
with difficulty	
☐ unable	ipsilateral shorter mm
	Trendelenburg (Tick one box only)
Distance walked (Tick one box only)	unable to test
unlimited, several hours	negative
six blocks, up to 2 km	indifferent
daily shopping, up to 500 m	positive
indoors only, up to 50 m	
bed / chair / not able to walk	Range of motion (neutral-zero-method)
Support (Tick one box only)	Flex / L Ext
none	
single cane for long walks	Abd // / Add
single cane most of the time	FR / / / / IR
☐ one crutch	ER L.J. / L.J. / L.J. IR
two canes	
two crutches or not able to walk	
Chains (T.) and because it	
Stairs (Tick one box only)	
foot over foot, with banister	
foot over foot, with banister	
in any manner	
unable	
Investigator's Signature:	Date: Day Month Year
Please fax this page a	as soon as completed

Plate # U81

Visit # 284 7 Year

Independent Review X-ray Follow-up

(page 1 of 2)

Project No.: I	R3		
Study Patient No:			

	" " "	
General Findings	Date of I	Radiograph: Day Month Year
	nm varus	sition ** anged s tilted
inclination	_	idence mm
Stem fixation/for uncemented stem not applicable	ems (Engh et al)	
fixation by bone ingrowth		
stable fibrous ingrowth		
unstable implant		
**Compared to baseline post-o	perative	
	r Classification) (Tick one box only)	
☐ Grade 0 none, no islands of bo		
	elvis or proximal end of the femur leaving	g at least 1 cm between opposing
Grade III bone spurs from the pone surfaces to less than 1 cr	pelvis or proximal end of the femur, reduc m	ing the space between opposing
Grade IV apparent bone ankylo	osis of the hip	
Notes:		
Investigator's Signature:		Date: Day Month Year
	Please fax this page as soon as complet	e

		R3 EU St	udy				
DataFax#107		te#093			it#284 7 Year		П
>∜smith&neph		Independer X-ray Fol (page 2	low-up	'	Project N		
Radiographic Evaluation							
Radiolucent lines Negative Omm 1mm 2mm >2mm Zone I	Osteolysis no yes	mo	derate severe mm >2mm		ertrophy minimalmodera e 1mm 2mm minimalmodera e 1mm 2mm minimalmodera e 1mm 2mm minimalmodera	te severe >2mm	1 7 2 6 3 5
Radiolucent lines Negative	Osteolysis no yes		derate severe mm >2mm		ertrophy minimal modera 1mm 2mm	te severe >2mm	V VI 8 14 9 13 12 11

AP Cup

AP Stem

Notes:

Investigator's Signature:

Please fax this page as soon as complete

Date: Day Month Year

Please fax this page as soon as complete

Clinical Follow-up (page 1 of 2)	Study Patient No:
Date of Ass	essment: Day Month Year
	Date of Ass

Please fax this page as soon as completed

Notes:

_						 		_		_														
_			-	(1)	-	 _	-	-	-	-	***	-			-					-				
		1000		100		100			200					1000										
	100			100												100								
		100				100					- 11													
	1000	100				1000			1000				1000	1000		10.00		1000						- 9
				1000											-		-		-	-	-	-	-	
																	+ 40							

Plate #070

Visit #320

-		
9.0	smith&nep	how
	Simulation	IICAA

Clinical Follow-up (page 2 of 2)

Project No:		R3
Study Patient No:		

		(15		2 323-243-243-243-243-243-243-243-243-243-	
	Years arris Hip Score				
	o pain (Tick one box only) none or ignores it slight, minimal; no compromise in act mild; following longer activities		Sitting (Tick one box of comfortably in a on a high chair unable to sit co	any chair 1 hour for 1 1/2 hour	
	moderate; some limitations of activitie marked; serious limitations of activitie disabled; no activities possible, bedric	s	Limp (Tick one box on none slight		
En	ter public transportation (Tick one box of yes, possible no, unable		☐ moderate ☐ severe	nce (Tick one box only)	
Pu	tting on shoes and socks (Tick one box with ease with difficulty unable		□ none □ ipsilateral longe □ ipsilateral short	er mm	
Dis	unlimited, several hours six blocks, up to 2 km daily shopping, up to 500 m indoors only, up to 50 m bed / chair / not able to walk		Trendelenburg (Tide unable to test negative indifferent positive Range of motion (neutral-zero-method)	
Su	none single cane for long walks single cane most of the time one crutch two canes two crutches or not able to walk		Flex Abd ER		Ext Add IR
Sta	foot over foot, without banister foot over foot, with banister in any manner unable				
Inv	estigator's Signature:	4.1-			Month Year
	Piease fax	uns page as	soon as complete	ea	

Plate # U81

Visit # 320 10 Year

Independent Review X-ray Follow-up

(page 1 of 2)

Project No.: F	₹3		
Study Patient No:			

5000	(page 1 61 2)
General Findings	Date of Radiograph: Day Month Year
migration medial r	Stem position ** unchanged varus tilted valgus tilted subsidence mm subsidence mm subsidence mm
stable fibrous ingrowth unstable implant **Compared to baseline post-o	perative
Heterotopic ossification (Brooke	r Classification) (Tick one box only)
☐ Grade 0 none, no islands of bo ☐ Grade I islands of bone within ☐ Grade II bone spurs from the p bone surfaces	the soft tissues about the hip elvis or proximal end of the femur leaving at least 1 cm between opposing pelvis or proximal end of the femur, reducing the space between opposing
Investigator's Signature:	Date: Day Month Year
	Please fax this page as soon as complete

I		I			I		I		Ī		Ī	Ī	ĺ	1	Ì	

Plate # 093

Visit # 320 10 Year

> smith&nephew

Independent Review X-ray Follow-up

(page 2 of 2)

Project No.:	R3		
Patient No:			

Radiographic Evaluation					
Radiolucent lines	Osteolysis	Atrophy		Hypertrophy	
Negative		ı 🗆		, . ,	
0mm 1mm 2mm >2mm	no yes				
Zone I 🔲 🔲 🔲					
Zone II 🔲 🔲 🔲]
Zone III					1 7
Zone IV 🔲 🔲 🔲					2 6
Zone V 🔲 🔲 📗					3 5
Zone VI 🔲 🔲 🔲					
Radiolucent lines	Osteolysis	Atrophy		Hypertrophy	4
Negative					
0mm 1mm 2mm>2mm	no yes	minimal modera none 1mm 2mm	te severe >2mm	minimal moderate se none 1mm 2mm >2	vere mm
Zone 1]
Zone 2					_
					_
					IV VI
Zone 7					8 14
Zone 8					9 13
Zone 9 🔲 🔲 🔲					
Zone 10					10 12
Zone 11] 11
Zone 12]
]]
			Ц		-
Notes:					
Investigator's Signature:			_	Date:	
	Plea	se fax this page as s	oon as co		Month Year
	Radiolucent lines Negative	Radiolucent lines	Radiolucent lines	Radiolucent lines	Radiolucent lines

				1	1				

Plate # 099

Missed Visit/ Telephone Follow-up

Project No:		R3
Study Patient No:		

	Telephone Follow-up	Patient No:				
Interval Missed: 3 Months 5 Years Use this form for subjects still on study	1 Year 3 Years D 7 Years 10 Years	Pate of Report: Day Month Year World Visit.				
Reason Missed: (Tick one box only)						
Illness	Patient contacted and is feeling fine but do	pes not want to be examined				
Patient on vacation	Long difficult traveling distances					
Patient moved	Business commitments					
Patient address unknown	Patient is non-compliant with study require	ements				
	Other, please specify:					
Contact the subject by telephone and confirm the information below. If during the discussion Serious Adverse Events are revealed, complete the Adverse Event and Serious Adverse Event case report forms. Record telephone contact in the medical notes.						
Telephone Follow-up						
Unable to contact subject by p	hone during the visit window (No furthe	er response required)				
Ask the following questions an						
1. Has any component of yo	our Smith & Nephew modular hip been i	removed since your last visit?				
Yes No						
Complete Adverse	Event Case Report Form					
2. Have you had any proble	ems with the study hip since the last visit	t to the clinic?				
Yes No						
Complete Adverse	e Event Case Report Form					
3. Do you expect to have the	e study device removed during the next	year?				
Yes No						
Request subject to	contact study coordinator following the ren	noval of device				
4. How satisfied are you wit	h your hip replacement?					
☐ Very satisfied ☐ S	Somewhat satisfied Somewhat dissatis	fied Very dissatisfied				
5. If you had to make the de	ecision again to undergo your hip replace	ement surgery, would you do it again?				
Yes No						
Investigator's Signature:		Date: Month Year				

Plate # 300

smith&nephew

Adverse Event

Project No:			R3
Study Patient No:			

Please complete ONE event form per complica Number each event sequentially beginning wit	h "01" Date of Onset: L. L. L. L. L. L. L. L. L. L. L. L. L.
Event No:	Day Month Year
Adverse Event	
Event / Diagnosis please specify: Severity (Tick one box only) mild moderate severe Serious (Tick one box only) no yes Involves operated side (Tick one box only) no yes not applicable	Outcome of complication (Tick one box only) resolved ongoing / unresolved death, date prosthesis in situ at date of death no, latest date known Removal or revision of component(s), date:
Relationship to study device (Tick one box only) definitely related	Day Month Year
probably related possibly related not related Relationship to study procedure (Tick one box only) definitely related probably related possibly related not related reatment none medication/orthotics	Components removed / revised femoral head femoral stem acetabular cup taper sleeve acetabular liner Hospital (inpatient or outpatient) / Readmission required? no yes, date of readmission:
Investigator's Signature:	Date: Day Month Year

